11.1.1 Patient- and dose-level summary AE tables

AEs will be classified into study phases as follows: dose escalation study visits, home doses, exit

DBPCFC, and overall. Specific AEs of interest, which will be included in the patient- and dose-level AE tables whether or not any patients experienced them, are listed under Secondary Endpoints in section 5.2 and under Derivation of Safety Variables in section 9.2.3. Any additional preferred terms recorded for at least one patient or dose will also be reported, listed alphabetically following the specific AEs of interest. AEs occurring and doses of study medication administered during both arms of the exit DBPBFC will be counted towards the totals. (Refer to mock Tables 3.1 and 3.2.)

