2.3 Risk/Benefit Assessment

2.3.1 Known potential risks

There is a significant rate of adverse reactions with peanut oral immunotherapy in clinical trials to date. Mild adverse reactions such as oral itching or nausea are reported in up to 10-15% of all doses. Over the course of an individual study, this reaches nearly 100% of all subjects. The rate of these adverse events are outlined in representative studies in Table 1.

More severe reactions requiring treatment with epinephrine or inhaled beta-agonists are less frequent but can occur. In a large review of multiple centers performing peanut OIT, Wasserman et al noted a total of 95 adverse reactions requiring epinephrine in 352 patients that collectively received more than 240,000 doses of peanut.²⁵ The results of the largest peanut OIT trial to date, a phase 2 clinical trial utilizing product AR101 were published in March of 2018.²¹ In this study, 9 (14%) of 63 subjects received a single injection of epinephrine during initial double blind placebo controlled food challenge (DBPCFC) at screening: 4 were randomized to AR101, 4 to placebo, and 1 was not enrolled. For the duration of maintenance therapy, one treatment subject received a single epinephrine injection for moderate anaphylaxis at home. Finally, during the exit DBPCFC, 11 of 26 placebo subjects (42%) were administered epinephrine and 2 of 23 AR101 subjects (9%) received a single injection of epinephrine.

Across the various peanut OIT trials, there has been no specific statistical analysis examining adverse reaction rate or withdrawal rate at various ages. Presumably this is due to the fact that no specific age related pattern has emerged and that anaphylaxis and subject withdrawal has occurred in subjects of all ages.

There is also a risk for development of Eosinophilic Esophagitis (EoE). A recent review estimated the prevalence across the OIT clinical trials as 3-4% and in the study conducted by Bird et al, EoE occurred in only 1 subject (<5%) from the treatment group.²¹ Once OIT is discontinued in these patients, the EoE typically resolves.

There is also a risk of causing anxiety or stress in the subject or the family. The impact of oral immunotherapy on quality of life has been examined with a variety of foods. Quality of life in patients with food allergy improves in some but declines in others while undergoing OIT, and in particular tends to decline in those rating a higher quality of life prior to initiation of the treatment.²⁶

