If a subject does not tolerate a dose increase, then the patient will be administered a dose reduced by 25%, with increase to the originally intended dose at the subsequent visit. If the patient still does not tolerate the dose, then the decision on how to proceed will be determined at the investigator's discretion. This may involve temporarily decreasing the subject's dose, making a smaller increase, or prolonging the duration of a given dose. If any subject is unable to reach the goal maintenance dose, then the investigator may decide to continue the subject on a lower maintenance dose for the duration of the study.

Table 6: Dose Escalation Schedule

Dose of Peanut Protein	Week of Protocol
6 mg	0
12 mg	2
25 mg	4
50 mg	6
75 mg	8
150 mg	10
300 mg	12

Home Dosing

All subjects will be offered the opportunity to continue once daily consumption of the maintenance dose after the end of their study participation. This ongoing maintenance therapy is optional and will not be paid for by the study. The subjects will be instructed to otherwise continue a peanut free diet.

Follow Up

The subject will also undergo a final oral food challenge at the final visit (SV10). This food challenge will be double blind and placebo controlled. A double blind placebo controlled food challenge (DBPCFC) is the gold standard for diagnosis of food allergy and is the standard utilized for most oral immunotherapy trials at exit.

Roasted peanut powder will be utilized for the challenge, with oat flour as placebo. An individual will undergo a standard challenge described below (Table 7) with either the roasted peanut or the placebo, blinded to both subject and investigators. The same individual will then undergo a second challenge with the opposite (either peanut or placebo) either later that day or by returning to clinic the following day. Each challenge will be performed by increasing doses up to a final dose of 1000 mg of peanut protein. The individual doses will be 25, 100, 200, 300, 600, and 1000 mg of peanut protein. The highest tolerated dose will be recorded. If a patient reacted to a dose lower than 25 mg of peanut powder during the initial Oral Food Challenge then they will be started at the dose lower than where the reaction occurred for the DBOFC.

A urine pregnancy test will be repeated on all females of child bearing potential before the DBOFC.

Table 7: Double blind oral food challenge to peanut or control oat (SV 10)

Time	Dose	Clinician Intervention *

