5.2 Endpoints

Primary Endpoints. Response to treatment defined as ability to successfully consume a single dose of 300 mg or greater of peanut protein with no dose limiting symptoms at exit double blind placebo controlled food challenge (DBPCFC).

The highest dose of roasted peanut protein tolerated by the subject at exit DBPCFC will also be compared to the highest dose tolerated at baseline.

The effect of boiled peanut immunotherapy on the immune response to peanut will be evaluated via specific serum markers of sensitization and tolerance to peanut.

- Levels of serum specific peanut IgE, with higher levels associated with greater likelihood of clinical reaction on exposure to peanut protein.

- Peanut protein component panel, to determine the presence of high levels of sensitivity to peanut proteins known to be associated with severe systemic reactions (Arah 1,2, 3) versus mild reactions (Arah8)
- Levels of peanut specific serum IgG4, with higher levels associated with increased tolerance to peanut protein

These markers will be evaluated at baseline and the conclusion of the study.

Secondary Endpoints. The rate of adverse events in the subjects receiving boiled peanut oral immunotherapy. Possible adverse events include: side effects of treatment defined as oral itching, rhinorrhea, conjunctivitis, urticaria, angioedema, abdominal upset, vomiting, diarrhea, cough, wheeze, or anaphylaxis

- Adverse events will be recorded in terms of the percentage of subjects with adverse events on initial escalation day and at dose escalation visits by CRU staff.
- Adverse events will also be recorded in terms of overall percentage of home doses that result in adverse reaction, with data compiled from home logs.

The adverse reactions will be graded in severity and the treatment required will be recorded.

Validated, age-specific, food-related quality-of-life surveys before and after peanut oral immunotherapy will be completed by all patients/families.

6 Study Methods

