8.2.3 Safety Population

- *All enrolled patients who took at least one dose of study medication during any dose escalation visit or at home, or participated in either arm of the exit DBPCFC.*

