11.1.2 Comparative AE table

AE data from this study will be compared descriptively to the AE data from three published studies: the study medication arms of the Phase 2 and Phase 3 trials of AR101 OIT for peanut allergy (Bird et al., 2018; Vickery et al. for PALISADE, 2018), and OIT data from the PACE meta-analysis study of OIT for peanut allergy (Chu et al., 2019). No hypothesis testing will be performed.

For this table, study AEs will be categorized into two study phases as best corresponds to the comparative data: 1) initial dose escalation study visit, and 2) an increasing dose phase which includes all other dose escalation study visits and home doses, but excludes the exit DBPCFC. AEs will be grouped into severity grades, treatments, and preferred terms, where the preferred term list will include the specific AEs of interest only (see sections 5.2 and 9.2.3). (Refer to mock Table 3.3 for comparative data and source information.)

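### The overall AE figures in SAP Tables 3.1 and 3.2 pool boiled peanut OIT with the roasted-peanut and oat exit challenge, so they are not the OIT adverse-event rate

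*SAP*

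**What the plan says.** SAP 11.1.1 sorts AEs in Table 3.1 (patients) and Table 3.2 (doses) into escalation visits, home doses, exit DBPCFC and overall. It then adds: "AEs occurring and doses of study medication administered during both arms of the exit DBPBFC will be counted towards the totals" (the abbreviation is evidently the DBPCFC). Protocol 6.1.2 describes that challenge: "Roasted peanut powder will be utilized for the challenge, with oat flour as placebo", and "Each challenge will be performed by increasing doses up to a final dose of 1000 mg of peanut protein". Neither arm contains the boiled peanut powder that Protocol 6.1.1 defines as the intervention.

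The secondary endpoint in SAP 5.2 is "The rate of adverse events in the subjects receiving boiled peanut oral immunotherapy". It is recorded through two measures: the share of children with AEs on the initial escalation day and at escalation visits, and the share of home doses followed by a reaction.

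Elsewhere the SAP keeps the challenge apart from treatment:
- Under SAP 8.2.3 a child enters the safety population if he or she "took at least one dose of study medication during any dose escalation visit or at home" or, as an alternative route, took part in either exit arm.
- The schedule in SAP 6.3, as far as the extracted table can be read, marks no study drug administration at the final visit.
- SAP 11.1.2 leaves the exit challenge out of comparative Table 3.3. For that table "the preferred term list will include the specific AEs of interest only".

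SAP 11.1 counts each child once within a category and divides dose-level counts by the doses given in that category. SAP 6.1 and 11.1.2 state that AE comparisons are descriptive, without testing.

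**The concern.** A line marked overall in the main AE tables is easily read as the safety summary of the treatment. Under the stated rule it is not. It adds a procedure that steps up roasted peanut to find the dose a child reacts to, and a placebo that should provoke nothing. The first can raise the numerator; both enlarge the dose denominator.

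The any-AE row is the least sensitive, because Protocol 2.2 expects nearly every OIT subject to have some AE. The rows that could mislead are the uncommon ones: less frequent terms, higher severity grades, and treatments such as epinephrine. These rows bear on the trial's hypothesis that boiled peanut is better tolerated. The prose names no patient-level total for all boiled peanut dosing that a reader could use instead.

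**Working it through.** The plan gives no figure to reproduce, so the check counts doses and then applies the protocol's own published rates.

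**1. Doses per completer.** Inputs: 5 doses on the initial escalation day (Protocol Table 5); 12 weeks of build-up (Table 6) plus at least 28 days before the exit challenge (synopsis), which is 112 days; 6 doses per exit arm (Table 7).
- Boiled doses = 5 + 111 daily doses up to the day before the exit visit = 116.
- Challenge doses = 2 × 6 = 12, of which 6 are oat.
- Share not boiled = 12/(116 + 12) = 12/128 = 9.4%.
- The schedule allows 14 to 17 weeks from initial escalation to exit. At 14 weeks: 12/(102 + 12) = 10.5%. At 17 weeks: 12/(123 + 12) = 8.9%. If the peanut arm stops at its first dose: 7/(116 + 7) = 5.7%.

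**2. Oat within the exit row.** One reaction in 6 peanut doses is 16.7%. With the oat arm pooled it is 1/12 = 8.3%.

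**3. General AE rates.** Ten completers give 1,160 boiled and 120 challenge doses. Overall rate = (r × 1,160 + k)/1,280, where r is the true OIT rate and k the number of exit doses with a reaction. Protocol Table 1 supplies two whole-course values of r; k from 0 to 4 is assumed.

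| r | k = 0 | k = 4 |
|---|---|---|
| 0.8% | 9.28/1,280 = 0.73% | 13.28/1,280 = 1.04% |
| 6.3% | 73.08/1,280 = 5.71% | 77.08/1,280 = 6.02% |

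Each further exit reaction dose adds 1/1,280 = 0.08 percentage points. One per child (k = 10) would bring 0.8% to 1.5%.

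**4. Epinephrine row.** Protocol 2.3.1 reports "95 adverse reactions requiring epinephrine in 352 patients that collectively received more than 240,000 doses of peanut" and, at the exit challenge of another trial, "2 of 23 AR101 subjects (9%) received a single injection of epinephrine". Exit events expected in 10 children = 10 × 2/23 = 0.87.
- *OIT rate per dose.* 95/240,000 = 0.0396% at most; × 1,160 = 0.46 events. Overall = (0.46 + 0.87)/1,280 = 0.104%. Ratio 0.104/0.0396 = 2.6; exit share 0.87/1.33 = 65%.
- *OIT rate per patient.* 95/352 = 0.27; × 10 = 2.70 events, or 2.70/1,160 = 0.233% of doses. Overall = (2.70 + 0.87)/1,280 = 0.279%. Ratio 0.279/0.233 = 1.2; exit share 0.87/3.57 = 24%.
- *Uncertainty in 2/23.* The exact 95% interval is 1.07% to 28.04%, that is 0.107 to 2.804 events in 10 children. The per-dose ratio then runs from 1.1 to 6.4. The per-patient ratio runs from (2.70 + 0.107)/1,280 ÷ 0.233% = 0.9 to (2.70 + 2.804)/1,280 ÷ 0.233% = 1.8.
- *Chance of at least one such exit event* = 1 − (21/23)^n: 52% if 8 children reach the exit challenge, 60% if 10 do.

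**5. Can the OIT figure be recovered?** At dose level, yes: add the escalation-visit and home-dose counts and denominators. At patient level a child may appear in both phases, so the counts cannot be added. Take the initial day as part of the escalation visits (as SAP 11.1.2 implies) and overall as the union of the three phases.
- The OIT count is exact if the escalation, home or exit count is zero.
- Otherwise it may not be. Counts of 2 (escalation), 2 (home), 2 (exit) and 4 (overall), with Table 3.3 showing 2 children on the initial day and 2 later, fit an OIT count of 2, 3 or 4 of 10. This supposes Table 3.3 is also given at patient level.
- For preferred terms outside the AEs of interest, Table 3.3 offers no help.

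**The case against.** The strongest reply is that the endpoint is already served. Both SAP 5.2 measures have their own phase rows, the published-data comparison excludes the challenge, nothing is tested, and the counting rule is openly stated. Protocol 8.3.4 requires all on-study AEs to be documented, so a total that includes a protocol procedure is an ordinary convention. All of this stands, and it confines the point to the overall figures and the pooled exit row.

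Second, recoverability. With 0.46 OIT epinephrine events expected, the Poisson chance of at most one is e^(−0.46) × 1.46 = 92%, and the patient-level count is then exact. This holds at the per-dose base rate. At the per-patient rate the same chance is e^(−2.70) × 3.70 = 25%, although the count is still exact if all events fall in one phase. The two rates therefore pull in opposite directions: where the inflation is small, recovery is less assured.

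Third, the 2.6-fold ratio. Its source averages 240,000/352 = 682 doses per patient against 116 here, and the first row of Protocol Table 1 shows far more AEs per dose in build-up (46%) than in maintenance (3.7%). This trial is mostly build-up, so the long-run per-dose rate probably understates its OIT rate. That is a fair criticism, and 2.6 should not be quoted without 1.2. The 1.2 in turn assumes that all of the source's events fall within a course as short as this one.

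Fourth, terminology. Protocol 6.2 lists roasted powder under investigational product management, so calling it study medication is arguable. That does not extend to treating either arm as boiled peanut OIT.

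Finally, the mock tables might contain a subtotal or footnote that settles the matter. This cannot be excluded.

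**Conclusion.** The point holds as a defect of definition and labelling that should be corrected. By the stated rule, the overall figures in Tables 3.1 and 3.2 are not the AE rate of boiled peanut OIT, and the exit and overall dose percentages are diluted by oat doses. No patient-level OIT total is named in the prose, and it cannot always be derived when escalation and home counts are both above zero.

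About 9% of a completer's counted doses are not boiled peanut. General AE rates move little, in either direction. For epinephrine use the overall dose rate could be about 1.2 to 2.6 times the OIT rate, with wide uncertainty. At patient level, overall can only equal or exceed the OIT count. These sizes assume full adherence, ten completers, all 12 challenge doses given, and published roasted-peanut epinephrine rates applying here.

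A reader might infer more than this. The documents do not support the view that the comparison with published roasted-peanut OIT is contaminated, since Table 3.3 excludes the challenge. Nor do they support the view that the SAP 5.2 measures are misreported, that overall always overstates AE rates, or that the OIT rate is lost: at dose level it follows from the phase rows.

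**What to change.** In Tables 3.1 and 3.2:
1. Add a total for all boiled peanut dosing (initial escalation, later escalation visits, home doses) at patient and dose level, and name it the OIT safety summary.
2. Report exit-challenge AEs and doses by arm, roasted peanut and oat, outside that total, and call them challenge doses. No exit AE is hidden.
3. If an overall figure is kept, label it as including the exit food challenge.

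The cost is a few sentences of SAP text and some extra columns in two table shells. Protocol 6.2 tracks the two powders separately, and SAP 9.2.1 refers to a CRF for the peanut arm, so the data appear to exist already; the AE form itself is not shown. Because both challenges may fall on one day, a simple rule is needed for assigning an AE to an arm.

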11.1.2 Comparative AE table

AE data from this study will be compared descriptively to the AE data from three published studies: the study medication arms of the Phase 2 and Phase 3 trials of AR101 OIT for peanut allergy (Bird et al., 2018; Vickery et al. for PALISADE, 2018), and OIT data from the PACE meta-analysis study of OIT for peanut allergy (Chu et al., 2019). No hypothesis testing will be performed.

For this table, study AEs will be categorized into two study phases as best corresponds to the comparative data: 1) initial dose escalation study visit, and 2) an increasing dose phase which includes all other dose escalation study visits and home doses, but excludes the exit DBPCFC. AEs will be grouped into severity grades, treatments, and preferred terms, where the preferred term list will include the specific AEs of interest only (see sections 5.2 and 9.2.3). (Refer to mock Table 3.3 for comparative data and source information.)

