- History of life threatening peanut anaphylaxis
- Asthma requiring more than medium dose inhaled corticosteroids for age per the National Heart, Lung, and Blood Institute Asthma Guidelines
- Cardiovascular disease
- Use of beta-blockers (oral), angiotensin converting enzyme inhibitors, angiotensin receptor blockers, or calcium channel blockers
- Use of steroid medications in the following manners:
 - Daily oral steroid dosing for greater than 1 month during the past year OR
 - Burst or steroid course in the past 3 months before inclusion OR
 - Greater than 2 burst oral steroid courses in the past year of at least 1 week duration
- Pregnancy or lactation
- Prior participation in food oral immunotherapy studies, including OIT, sublingual immunotherapy (SLIT), or epicutaneous immunotherapy (EPIT)
- Eosinophilic gastrointestinal disease
- Oat allergy, as oat flour is the vehicle with which study drug may be mixed for purposes of blinding and will be used as placebo for the exit DBPCFC

	
• History of food protein-induced enterocolitis syndrome (FPIES)• History of developmental delay or speech delay that precludes age-appropriate communication, in the opinion of the investigator
Description of Sites and Facilities Enrolling Patients:	Screening will be performed at the Cleveland Clinic main campus and satellite outpatient clinic locations. Any patients identified as eligible will be referred to main campus for further evaluation and possible enrollment.
Description of Study Intervention:	Oral Immunotherapy will be administered utilizing a powder derived from boiled peanuts. Treatment will begin with an initial escalation day in which dosing is begun at 0.1 mg peanut protein and escalated to a final dose of 6 mg peanut protein. Doses are ingested orally. The subjects will continue daily oral ingestion of doses at home and return for updosing every 2 weeks to a final maintenance dose of 300 mg peanut protein. The subjects will continue daily oral ingestion of the peanut product for a minimum duration of 28 days before undergoing exit DBPCFC. At the conclusion of the study, patients will be offered continued maintenance therapy off study in line with current specialty standards.
Study Duration:	18 weeks
Participant Study Duration:	18 weeks

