Though immunotherapy can be administered in a variety of methods, oral immunotherapy (OIT) has shown the most promise in the treatment of food allergy. Several recent trials have utilized the technique of oral immunotherapy for treatment of peanut and other food allergies. This therapy involves mixing the food allergen into a vehicle of choice and having the subject begin daily consumption while gradually increasing the dose. Several endpoints have been defined when evaluating the response to immunotherapy. Desensitization results in a higher threshold for an allergic reaction, typically above the amount that will be encountered in an accidental exposure. However, this does require ongoing dosing. The most desirable outcome of OIT is sustained unresponsiveness, or continued long term tolerance of the food without the need for daily maintenance therapy.

Although individual responses vary considerably, OIT will induce significant desensitization in most subjects who are able to tolerate the therapy. However, these studies are limited by frequent treatment related AEs and high rates of withdrawal due to these AEs. The reported AEs and dropout rates from representative studies are outlined in Table 1.⁸⁻¹⁶

There is a large amount of heterogeneity in the reporting of AEs. More specifically, AEs are at times reported in terms of the percent of subjects experiencing an adverse reaction. At other times, adverse reactions are reported in terms of the percent of doses that cause an AE. This method is often utilized to report AEs during maintenance dosing. This is in part due to the fact that over the course of all phases of an individual study and when including mild AEs in addition to more significant reactions, nearly 100% of patients have some form of AE during treatment. Thus it may be more meaningful to report the percent of doses causing symptoms at times.

Table 1: Prior OIT Trials

Author	N	Age	Design	Adverse Events	Drop outs	Additional Detail on Drop Outs
Jones et al 2009 [8]	39	1-16	Open label	92% of subjects on initial escalation day, 46% doses during build up, 3.7% doses during maintenance	10 (25%)	4 withdrew for allergic effects and 6 for personal reasons
Hofmann et al 2009 [10]	28	1-16	Open label	93% of subjects on initial escalation day, 46% doses during build up, 3.5% of doses during maintenance	5 (18%)	3 withdrew following initial escalation, 1 during build up, 1 during maintenance

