6.3 Study Assessments

The study Schedule of Activities as provided in section 1.3 of the protocol is as follows.

Visit		Study Visit 1	Study Visit 2 Visit 1 +1-4 weeks	SV 3 Visit 2 +2 weeks	SV 4 Visit 2 +4 weeks	SV 5 Visit 2 +6 weeks	SV 6 Visit 2 +8 weeks	SV 7 Visit 2 +10 weeks	SV 8 Visit 2 +12 weeks	SV 9 Visit 2 +14 weeks	SV 10 Visit 1 +18 weeks

Procedures		Enrollment/Baseline visit	Oral Food Challenge	Initial dose escalation	Dose escalation visit 1	Dose Escalation Visit 2	Dose escalation visit 3	Dose escalation visit 4	Dose escalation visit 5	Dose escalation visit 6	Dose escalation visit 7	Oral Food Challenge
Informed Consent	X											
Demographic s	X											
Vitals	X	X	X	X	X	X	X	X	X	X	X	X
Spirometry*	X		X	X	X	X	X	X	X	X	X	X
Blood Draw			X									X
Skin prick test			X									X
Oral food challenge		X										X
Urine Pregnancy	X											X
Study Drug Administratio n			X	X	X	X	X	X	X	X	X	
Study Drug Compliance				X	X							
AE Review			X	X	X	X	X	X	X	X	X	X
Conmed Assessment	X	X	X	X	X	X	X	X	X	X	X	X
FAQL Questionnaire	X											X

Due to the difficulties of scheduling study visits during the COVID-19 pandemic, the primary analysis will not place any limitations on the timing of study visits. All study visits will be analyzed in order by date, and the number of days from initial oral food challenge (OFC) and initial dose escalation visit will be reported for each study visit. If more than seven dose escalation visits are required as described in the study protocol section 6.1.1 'Study Intervention Description', the additional study visits will be named 'Additional Study Visit 9.1' through 'Additional Study Visit 9.x' for the purposes of analysis and reporting.

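### The comparative AE table counts maintenance home doses in its increasing dose phase, so dose-level rates mix phase composition with any effect of boiling

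*SAP*

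**What the plan says.** SAP 11.1.2 sets this trial's AEs beside three published sources on roasted-peanut OIT: the active arms of the AR101 Phase 2 and Phase 3 trials, and a meta-analysis. It explains the layout by saying that "study AEs will be categorized into two study phases as best corresponds to the comparative data". The first phase is the initial dose escalation visit; the second is "an increasing dose phase which includes all other dose escalation study visits and home doses, but excludes the exit DBPCFC". For the comparator figures it says "Refer to mock Table 3.3 for comparative data and source information", and it adds "No hypothesis testing will be performed".

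The protocol's dosing has a third part. Table 6 reaches 300 mg at week 12. The synopsis, directly after describing updosing to the 300 mg maintenance dose, says: "The subjects will continue daily oral ingestion of the peanut product for a minimum duration of 28 days before undergoing exit DBPCFC". Protocol 6.1.2 also allows maintenance below target: "If any subject is unable to reach the goal maintenance dose, then the investigator may decide to continue the subject on a lower maintenance dose".

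The other AE tables do not make the distinction either. SAP 6.3.3 and 11.1.1 use escalation visits, home doses, exit challenge and overall, with all home doses in one phase. Under SAP 11.1, dose-level percentages are divided by all doses given in the category, and patient-level counts take each child once.

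**The concern.** Once a child settles at a maintenance dose, the dose no longer rises, yet those days stay in the denominator of the increasing dose phase. If maintenance doses react less often than build-up doses, adding them lowers the dose-level rate whether or not boiling does anything.

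The protocol's own background makes this plausible. In its Table 1, one open-label study is summarised as "92% of subjects on initial escalation day, 46% doses during build up, 3.7% doses during maintenance". A second open-label study gives 46% and 3.5%, and a third study gives 7.8% of doses in a rush protocol and 2.9% in maintenance.

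Comparing AE rates with published roasted OIT is the secondary objective (SAP 5.1), and lower AE rates are part of the central hypothesis (Protocol 4.1). SAP 5.2 expresses the home-dose endpoint as a percentage of doses, which is the measure that phase mix affects. A reader of Table 3.3 could take a difference in phase composition for an effect of boiling, and the planned tables would not let that reader check.

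**Working it through.** The plan states no figure for this comparison. Its only design figure, the power of the primary test, does not bear on it.

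**1. Maintenance share of the phase.** Assume one dose a day and none missed.
- Build-up: 12 weeks (Table 6) = 84 doses after the initial escalation day.
- Maintenance at the synopsis minimum: 28 doses. Share w = 28/(84 + 28) = 25.0%.
- From the visit schedule: exit is at Visit 1 + 126 days, Visit 2 falls 7 to 28 days after Visit 1, and 300 mg is reached 84 days after Visit 2. The gap is 126 − 28 − 84 = 14 to 126 − 7 − 84 = 35 days. Counting from the day after the last increase to the day before exit gives 13 to 34 doses, so w = 13/97 = 13.4% to 34/118 = 28.8%.

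The 28-day minimum and exit at Visit 1 + 18 weeks fit together only if Visit 2 falls within 126 − 84 − 28 = 14 days of Visit 1, whereas the schedule allows up to 4 weeks. These statements need reconciling.

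**2. Effect on a dose-level rate.** Pooled rate = (1 − w) × build-up rate + w × maintenance rate. The rates are from Protocol Table 1 and show size only; none is from an SAP comparator.

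| Maintenance doses | w | 46% / 3.7% pools to | 7.8% / 2.9% pools to |
|---|---|---|---|
| 13 | 13.4% | 40.3% (−12%) | 7.1% (−8%) |
| 28 | 25.0% | 35.4% (−23%) | 6.6% (−16%) |
| 34 | 28.8% | 33.8% (−27%) | 6.4% (−18%) |

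For example, 0.75 × 46 + 0.25 × 3.7 = 34.5 + 0.925 = 35.4%. The changes in brackets are relative to the first rate of each pair.

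**3. Effect on the comparison.** Give boiled and roasted peanut identical true rates (46% and 3.7%), fix the boiled share at 25%, and vary the comparator's share:

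| Comparator maintenance share | Boiled | Roasted | Ratio |
|---|---|---|---|
| 0% | 35.4% | 46.0% | 0.77 |
| 25% | 35.4% | 35.4% | 1.00 |
| 50% | 35.4% | 24.9% | 1.43 |
| 75% | 35.4% | 14.3% | 2.48 |

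With no true difference, the table could favour boiled peanut, be neutral, or go against it.

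**4. Patient-level counts.** The chance of at least one AE over n independent doses is 1 − (1 − p)^n. At an assumed 1.2% per dose it is 63.7% over 84 doses and 74.1% over 112. At an assumed 1.2% in build-up and 0.3% in maintenance it goes from 63.7% to 66.7%. Adding doses cannot lower this figure.

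**The case against.** The strongest defence is that the SAP chose its two phases to match the comparators. If their published figures also run from the first updosing step through maintenance, pooling is the right match, and a split alone would make the comparison worse. Protocol 2.3.1 shows that the AR101 Phase 2 trial had maintenance therapy. The mock tables are not in the text available for this review, so they can be assumed neither to cure the problem nor to confirm it.

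A reader might infer that the table leans toward boiled peanut, perhaps by about a quarter. The documents do not support that:

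- The direction depends on each comparator's maintenance share, which is not given.
- Dilution applies only to dose-level percentages. SAP 11.1.2 does not say which unit Table 3.3 uses, and the AR101 AE results quoted in Protocol 2.2 and 2.3.1 are per patient.
- Only two of the nine Table 1 rows give separate build-up and maintenance rates, and a third gives rush and maintenance. Several rows pool phases, and one study reports 1.2% of doses in build-up, below the maintenance rates of other rows. A twelvefold fall is not general.
- Visit timing cuts both ways. SAP 6.3 says "the primary analysis will not place any limitations on the timing of study visits". A late exit lengthens maintenance, but extra escalation visits lengthen build-up. The schedule already lists a seventh escalation visit at Visit 2 + 14 weeks. If it carried an increase, the gap to exit would be at most 126 − 7 − 98 = 21 days, or 20 doses, and w at most 20/118 = 16.9%.

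The comparison is also descriptive, in ten children.

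These points remove any claim about direction or a definite size. They leave the labelling, the pooling and the missing split. An intention to match does not tell the reader which phases each figure covers, and one two-phase scheme serves two trials and a meta-analysis.

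**Conclusion.** The point holds as one of composition, not of known bias. The increasing dose phase contains constant-dose maintenance doses: about a quarter on the planned schedule, about 13% to 29% from the visit schedule, and fewer if build-up runs past week 12. No planned AE table lets a reader see them apart. A dose-level percentage for that phase therefore depends on the maintenance share as well as on any effect of boiling.

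The percentage is diluted if maintenance doses react less often, as in the Table 1 studies that give both rates. The comparison then favours boiled peanut only where the comparator's share is smaller. With a larger share it goes the other way, and patient-level counts are never diluted. The pooled values assume daily dosing with none missed and borrow rates from studies outside the SAP's comparator set, so they are illustrations and not estimates of bias in this trial.

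Nothing here touches the primary endpoint. It is a low-cost improvement to the secondary-objective comparison.

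**What to change.** In SAP 11.1.2 and Table 3.3, and for home doses in Tables 3.1 and 3.2:

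1. Show build-up and maintenance separately beside the pooled figure, with the number of doses in each.
2. Start maintenance after each child's last dose-increase attempt, whether or not it was tolerated. Splitting at the first day on the eventual maintenance dose would not work: a child who reacts to an increase and is then kept on a lower dose first took that dose earlier, so the reaction would be counted as maintenance.
3. For a child who stops before a maintenance dose is settled, keep all home doses in build-up.
4. For each comparator figure, state which phases it covers and whether its unit is patients or doses, unless mock Table 3.3 already does so. Set it beside the matching boiled-peanut figure, using the pooled figure where the source pools.

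The data should already exist. The home log (Supplement 2) records the date and dose of each intake, and Table 4.1 lists the maximum tolerated dose and the home dose by visit. Before finalising, check that the study drug administration form also dates failed increases. The cost is SAP wording, one derived date per child and slightly more tabulation, with smaller denominators per phase in a descriptive ten-child study.
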